1.2.5.4 Infections

BOS161721 is expected to diminish the activity of T-cell, B-cell and NK-cell lines. Like other medications modulating immune response, BOS161721 may increase the potential risk for infection, including serious infections. IL-21 produced by CD4⁺ Th cells is required to sustain the anti-viral function of CD8⁺ T-cells against chronic viral infections. Nonclinical evidence suggests that the risk of chronic viral infection recurrence or increased severity may occur with IL-21 inhibition.³⁵

These conditions will be fully characterized with clinical descriptions and routine laboratory and/or specialty testing and treated where indicated with appropriate local standard of care.

Patients with a history of opportunistic infection, including recurrent or severe disseminated herpes zoster or disseminated herpes simplex within the last 3 years, or any other underlying pathology predisposing to serious infection, are excluded from studies with BOS161721 (for further details please refer to the current IB for BOS161721).

Patients will be assessed for hepatitis B, and C, and HIV-1/2 combination, at screening.

Cryptosporidium Infection

Cryptosporidium infection was noted in patients with an IL-21 receptor loss-of-function gene mutation and similar findings of cryptosporidium infection have been observed in immunosuppressed liver transplant and human immunodeficiency virus patients.^{36,37} Since BOS161721 is expected to diminish the immunosurveillance activity of T-cell, B-cell, and NK-cell lines, a similar risk is biologically plausible with prolonged exposure to BOS161721.

Since the risk of opportunistic cryptosporidium infection increases with low levels of CD4⁺ T-cells,³⁷ patients with a CD4⁺ count < 500 cell/mm³ were excluded from the Phase 1 SAD study (BOS161721-01), and CD4 + < 350 cells/mm³ will be excluded from the MAD/POC parts of the study. Patients exposed to investigational product who develop diarrhea during the course of the study should immediately undergo an assessment for opportunistic infection including stool for ova and parasites and stool examination for cryptosporidium. Positive cryptosporidium in stool sample at screening is an exclusion. Treatment by the investigator where indicated should be guided by findings and be consistent with local standard of care.

Based on the Phase 1 SAD study (BOS161721-01), infections in subjects who received BOS161721 was not observed.

1.2.5.5 Malignancy

The stimulatory effect of IL-21 on NK cells and CD8+ T-cells suggests the cytokine may have anti-tumor activity. Nonclinical studies have demonstrated significant anti-tumor effects of IL-21 in a number of tumor models. IL-21 therapy of human metastatic melanoma and renal cell carcinoma has demonstrated POC with significant increases in levels of perforin, granzyme B, and interferon gamma (IFN γ) expression in CD8+ T-cells and NK T-cells. Clinical response has been limited in these generally unmanageable diseases.

The impact of treatment with anti-IL-21 therapy on the development or growth of malignancies is not known; however, as with other immunomodulatory biologic agents, treatment with BOS161721 may result in an increase in the risk of malignancies. NK cell suppression by IL-21 neutralization may represent a biological mechanism for a potential risk for malignancy. Patients with a history or current diagnosis of cancer within the past 5 years, with the exception of non-melanoma skin cancer or cervical cancer in situ treated with apparent success with curative therapy, are excluded from the study.

Based on the Phase 1 SAD study (BOS161721-01), malignancy in subjects who received BOS161721 was not observed.

1.2.5.6 Hepatic Function Abnormality

There is no substantial evidence suggesting BOS161721 is associated with liver function abnormality. However, as a precaution, patients with a history of abnormal alanine aminotransferase (ALT) and/or aspartate aminotransferase (AST), or bilirubin at screening (ALT/AST > 2 \times upper limit of normal [ULN]; total bilirubin > 1.5 \times [ULN] and judged by the investigator to be clinically significant) were excluded from the Phase 1 SAD study (BOS161721-01), and will be excluded from this trial. Patients with a positive hepatitis B or C test or a history of alcohol dependence will also be excluded.

Based on the Phase 1 SAD study (BOS161721-01), hepatic function abnormality in subjects who received BOS161721 was not observed.

1.2.5.7 Failure of Vaccination

IL-21 is a key cytokine in development of B-cells into immunoglobulin-secreting plasma cells. Abnormal signaling through the IL-21R/Janus Kinase (JAK)3/signal transducer and activator of transcription (STAT3) pathway leads to defective humoral immune responses to both T-dependent and T-independent antigens and impairs the establishment of long-lasting B-cell memory. Abnormal signaling through the pathway has been related to decreased specific antibody responses following vaccination, and to increased susceptibility to encapsulated bacterial infections.³⁸

The effect of BOS161721 was evaluated in *in vivo* single dose studies in Cynomolgus monkey in which the animals received vaccination to T-cell dependent KLH antigen to stimulate a TDAR. These *in vivo* studies demonstrated that BOS161721 significantly inhibited B-cell proliferation and IgG antibody responses to the KLH protein antigen in a dose-dependent fashion; however,

BOS161721 administration did not affect anti-tetanus toxoid antibody data for IgM, IgG, IgG1, or immunoglobulin E (IgE) during the dosing phase in the same study.

1.2.5.8 Potential for Drug-Drug Interactions

Drug-drug interactions were not evaluated in the Phase 1 SAD study (BOS161721-01), which included only healthy adult subjects. Use of prescription medications (with the exceptions of oral contraceptives), and over-the-counter (OTC) treatments including herbal supplements such as St John’s Wort (except multivitamins), in the 2 weeks prior to screening was prohibited in the SAD study.

See [Section 4.5](#) for other specific exclusion criteria which support lowered risk of interactions, and [Section 4.6.1](#) for corticosteroid (CS) dosing. In addition, [Section 1.2.5.6](#) describes considerations for hepatic function for this study.

1.2.5.9 Potential Risk to Fetal Development

No data on preclinical reproductive toxicity are available at the time of this study.

2 STUDY OBJECTIVES AND ENDPOINTS

This trial has separate objectives and endpoints for the MAD Phase 1b and POC Phase 2 portions of the study. The primary, secondary, and exploratory objectives for each phase, as applicable, are described below with their corresponding endpoints.

2.1 Phase 1b Multiple Ascending Dose

OBJECTIVES	ENDPOINTS
Primary	

 To assess safety, tolerability, and immunogenicity of repeat doses of BOS161721 (20, 60, and 120 mg) administered SC in adult patients with moderately to severely active SLE on limited background standard of care treatment, in order to estimate the optimal dose. 	Safety Endpoints 
 Incidence and severity of AEs and SAEs, related AEs, AEs leading to study drug discontinuation, AEs by severity and relatedness Injection site reactions Columbia Suicide Severity Rating Scale (C-SSRS) 12-lead ECGs parameter results at each visit and change from baseline Vital signs (blood pressure [BP], heart rate, and temperature) parameter results at each visit and change from baseline Clinical laboratory results and change from baseline Physical examinations changes from baseline ADAs Study drug exposure/compliance
Secondary	

 To characterize the PK of BOS161721 and select the optimal dose of BOS161721 based on safety, PK, and PD effects in patients with moderately to 	Pharmacokinetic Endpoints 
 BOS161721 concentration by visit and time point Maximum observed concentration (C_{max}), T_{max}, area under the concentration-time curve (AUC), terminal elimination

severely active SLE.
	
half-life ($t_{1/2}$), systematic clearance (CL), volume of distribution (V_d)
 
Pharmacodynamic Endpoints
 
 • Results and changes (or shifts) from baseline to each visit in phosphorylated signal transducer and activator of transcription 3 (pSTAT3), C3 and C4 levels, and leukocyte immunophenotype • Results and changes (or shifts) from baseline in anti-double-stranded DNA (dsDNA), antinuclear antibodies (ANA), anti-Sjögren syndrome A and B (SSA, SSB), Smith (Sm), and antiphospholipid (APL) autoantibodies at each visit • Results and changes (or shifts) from baseline in abrogation of IL-21 gene signature at each indicated visit

Exploratory
	

 • CCI [REDACTED] 	
 • CCI [REDACTED] • CCI [REDACTED]

 • CCI [REDACTED] 	
 • CCI [REDACTED]

 • CCI [REDACTED] 	
 • CCI [REDACTED]

2.2 Phase 2 Proof of Concept

OBJECTIVES	ENDPOINTS
Primary	

 To demonstrate a superior effect of BOS161721 at the chosen dose compared with placebo for response on the SRI-4 	Primary Efficacy Endpoint 
 The proportion of patients with a SRI-4 response at Day 210 (see Section 6.3.4.1)
Secondary	
To demonstrate a superior effect of BOS161721 at the chosen dose compared with placebo for response on clinical indicators of SLE activity, in adult patients with moderately to severely active SLE on limited background standard of care treatment	Secondary Efficacy Endpoints 
 The proportion of patients with: 
 SRI-4 response at each visit SRI-5 and SRI-6 response at each visit (Section 6.3.4.2) a sustained reduction of oral corticosteroid (CS) (≤ 10 mg/day and \leq Day 0 dose) between Day 120 and Day 210 new BILAG A flare or > 1 BILAG B flares relative to baseline through Day 210 PGA worsening a BICLA response a CLASI response medication failures Results and changes from baseline in: 
 CLASI swollen and tender joints ACR-28 SLEDAI-2K SLICC/ACR damage index Time to medication failure Duration of longest SRI-4 response Time to first SRI-4 response Time to BILAG A flare or > 1 BILAG B flare compared to baseline through Day 210
Safety	

 To assess safety and tolerability of repeat doses of BOS161721 at the chosen dose administered SC in adult patients with moderately to severely active SLE on limited background standard of care treatment 	Safety Endpoints 
 Incidence and severity of adverse events (AEs) and serious adverse events (SAEs), related AEs, AEs leading to study drug discontinuation, AEs by severity and relatedness Injection site reactions C-SSRS 12-lead ECGs parameter results at each visit and change from baseline Vital signs (blood pressure [BP], heart rate, and temperature) parameter results at each visit and change from baseline Clinical laboratory results and change from baseline Physical examinations changes from baseline ADAs Study drug exposure/compliance

Exploratory

• CCI [REDACTED]	
• CCI [REDACTED]

• CCI [REDACTED]	
• CCI [REDACTED]

• CCI [REDACTED]	
• CCI [REDACTED]

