 - i. “BILAG A:” Severe Arthritis, (BILAG item number 41), manifested by observed active synovitis in \geq 2 joints with marked loss of functional range of movements and significant impairment of basic activities of daily living that has been present on several days cumulatively over the past 30 days, including at the time of the screening visit. See [APPENDIX 5](#) for additional detailed specifications.
 - Basic ADLs are defined as the following activities which require assistance or assistive devices, (at least 1 must be present and documented in source):

- Ambulation, toileting, grooming- including bathing and dressing; feeding oneself
- ii. “BILAG B:” Moderate Arthritis, Tendonitis or Tenosynovitis, (BILAG item number 42), defined as tendonitis/tenosynovitis, or active synovitis in ≥ 1 joint, (observed or throughout history), with some loss of functional range of movements manifested by effects on instrumental ADLs such as:
 - Cooking, driving, using the telephone or computer, shopping, cleaning, etc., and has been present on several days over the last 30 days, and is present at the time of the screening visit

If only one “B” and no “A” score is present in the mucocutaneous body system or in the musculoskeletal body system due to arthritis, then at least 1 “B” must be present in the other body systems for a total of 2 “B” BILAG body system scores

8. Patients must be currently receiving at least 1 of the following:
 - a. Administration for a minimum of 12 weeks, and a stable dose for at least 56 days (8 weeks prior to signing consent) of the following permitted steroid-sparing agents:
 - i. Azathioprine (AZA), mycophenolate mofetil or mycophenolic acid, chloroquine, hydroxychloroquine, or methotrexate (MTX)
 - b. Prednisone (or prednisone-equivalent) cannot exceed 30 mg/day at screening for a patient to be eligible and must be stable at a maximum of 10 mg/day for at least 5 days prior to Day 0 (randomization) (see [APPENDIX 3](#))
9. Women of childbearing potential (WOCBP; see [Section 4.7](#) for full information regarding WOCBP, definition of menopause, and contraception):
 - a. Must have a negative serum pregnancy test at screening. Urine pregnancy test must be negative prior to first dose
 - b. Must not be breastfeeding
 - c. Must agree to follow instructions for method(s) of contraception for the duration of treatment with study drug plus 52 weeks

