4.6.1 Corticosteroid

Prior to randomization, oral CSs (prednisone or prednisone equivalent), may be used in accordance with the investigator's clinical judgment and best standard of care. See [APPENDIX 3](#) for examples of equivalents.

A maximum daily dose of 30 mg/day of oral CS will be acceptable for eligibility for the study, however, the daily dose must be tapered down to a maximum of 10 mg/day for at least 5 days prior to Day 0 (randomization day).

Tapering of steroids during the course of the study will be highly encouraged and should be evaluated at the protocol permitted visits (Day 0 through Day 60 and Day 120 through Day 150). Between Day 60 and Day 120, and between Day 150 and Day 210, oral CS doses must be held constant due to the endpoint evaluations occurring at Day 120 and Day 210.

- Once a patient has received the first dose of study drug (after Day 0), prednisone (or prednisone equivalent) dose is highly encouraged to continue tapering down as appropriate. The investigator should evaluate the prednisone dose at each visit and make the decision, within the protocol allowed windows.
 - Exception: Between Day 60 and Day 120, and between Day 150 and Day 210 (ie, within 60 days of primary and secondary endpoint assessments), oral CS doses must be held constant.

After Day 0 (first dose of study drug), a maximum of 1 oral CS “burst” for increased SLE disease activity will be allowed between Day 0 and Day 60, according to the following:

- The oral CS dose is allowed to increase to ≤ 40 mg/day of prednisone or equivalent, which must be tapered down to ≤ 10 mg/day within 2 weeks of initiation of the “burst”

- Alternatively, a single intramuscular (IM) dose of methylprednisolone (40 mg or equivalent) is permitted
- No increase of oral CS above baseline is permitted beyond Day 60

Treatment with inhalational CS therapy (eg, for asthma), or by any other route, but systemic administration, is allowed.

Treatment with intra-articular or intravenous CS is prohibited during the course of the study.

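### The secondary endpoint named as a sustained oral corticosteroid reduction requires no reduction, so it mainly measures absence of escalation and cannot show steroid sparing

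*Protocol*

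**What the plan says.** Section 2.2 of the Protocol places the endpoint among the Phase 2 secondary efficacy proportions. The name is "a sustained reduction of oral corticosteroid (CS)". The criterion is two ceilings, 10 mg/day and the Day 0 dose, the second with its window reading "Day 0 dose) between Day 120 and Day 210". No minimum decrease and no minimum starting dose is given.

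The rules that govern the dose are elsewhere:

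- Section 4.4, criterion 8: "Patients must be currently receiving at least 1 of the following". The options are a steroid-sparing agent or prednisone, so a patient can enter on no oral CS. For prednisone, the dose "must be stable at a maximum of 10 mg/day for at least 5 days prior to Day 0 (randomization)".
- Section 4.6.1, tapering: "Tapering of steroids during the course of the study will be highly encouraged". It is not mandatory.
- Section 4.6.1, hold periods: "Between Day 60 and Day 120, and between Day 150 and Day 210, oral CS doses must be held constant".
- Section 4.6.1, burst: at most one, which "will be allowed between Day 0 and Day 60, according to the following". An oral burst may reach 40 mg/day and must come down to 10 mg/day or less within 2 weeks.
- Section 4.6.1, later doses: "No increase of oral CS above baseline is permitted beyond Day 60".

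Section 8.2.3 classes prohibited medication and unallowable CS use under Section 4.6 as medication failure. Section 2.2 lists the proportion of medication failures and the time to medication failure as separate secondary endpoints. Section 8.2.3 applies the primary endpoint's superiority hypothesis to the secondary endpoints, and Section 8.2.4 assigns Pearson's chi-squared test to binary ones.

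**The concern.** The name and the definition disagree. The name promises a reduction, but the definition is met by staying at or below a ceiling that entry and conduct rules already impose. Two patients with opposite histories, one who tapered from 10 mg to 2 mg and one who stayed at 10 mg, score the same. So does a patient who never took a steroid.

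The report could then show a high sustained-reduction rate in both arms, which a reader would take as evidence about steroid sparing. A true difference between arms in how many patients cut their dose would leave no trace in the endpoint. What the endpoint does register, failure to stay at or below the Day 0 dose, is for the most part already counted as medication failure.

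**Working it through.** **The plan's own figure.** The Protocol states no rate, effect or power for this endpoint. Its only power statement (Section 8.1) is for SRI-4: 132 patients, 2:1 (88 and 44), 65% vs 40%, two-sided 0.10, more than 80%. With pooled rate (44×0.40 + 88×0.65)/132 = 0.567, null SE √[0.567×0.433×(1/44 + 1/88)] = 0.0915 and alternative SE √[0.24/44 + 0.2275/88] = 0.0897, z = (0.25 − 1.645×0.0915)/0.0897 = 1.11, so power is 86.6%. The statement holds. It does not bear on the CS endpoint, but it supplies the sample size and alpha used below.

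**Logic check, natural reading.** Read baseline as Day 0 and the post-Day 60 rule as no dose above it. Let d0 be the Day 0 dose (0 to 10 mg), d60 the dose held from Day 60 to Day 120, and d150 the dose held from Day 150 to Day 210 after any taper in Days 120–150. The rules give d150 ≤ d60 ≤ d0 ≤ 10, which is the endpoint criterion.

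Counting whole-milligram paths, each d0 allows (d0+1)(d0+2)/2 of them. Summed over d0 = 0 to 10 this is 286, and all 286 meet the endpoint. They include 11 paths with no change at any time (one per d0), one of which is 0 mg throughout.

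**Logic check, looser reading.** A burst need only come down to 10 mg/day, not to the Day 0 dose. Suppose the post-Day 60 rule bars only new increases, so that d60 may be anything from 0 to 10 mg whatever d0 was. There are then 11 × 66 = 726 paths, of which 286 meet the endpoint and 440 fail. The 11 unchanged paths still count as responses.

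**What the test sees.** If a share v of patients in an arm exceed the ceilings and the rest comply (natural reading), the arm's rate is 1 − v, whatever share truly reduced. For assumed v of 0% to 20%, that is 100% to 80%. Exact Pearson chi-squared rejection probabilities at two-sided 0.10, all rates assumed:

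| Quantity tested | Patients | Rates | Rejects |
|---|---|---|---|
| Endpoint as written, equal escalation | 88:44 | 95% vs 95% | 9.7% |
| Endpoint as written, less escalation on active | 88:44 | 95% vs 85% | 63% |
| True reduction, all evaluable | 88:44 | 40% vs 20% | 77% |
| True reduction, half on CS at Day 0 | 44:22 | 40% vs 20% | 50% |

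The normal approximation gives 76% for the third row. The first two rows depend only on escalation. The Protocol does not say what share of patients will be on oral CS at Day 0.

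**The case against.** Three stronger readings are tempting, and the Protocol does not support them.

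*Every compliant patient is a responder.* This depends on how Section 4.6.1 is read. A patient on 5 mg at Day 0 who has a late burst, tapers to 10 mg and then holds satisfies the burst and hold statements but exceeds the Day 0 dose. Whether that patient is compliant turns on the no-increase statement, which is not reconciled with the burst taper. The objection stands against the word every. It does not rescue the endpoint, because unchanged-dose and never-steroid patients respond under either reading.

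*The endpoint is the complement of medication failure.* It is not. Medication failure covers all of Section 4.6, including intra-articular and intravenous CS and new immunosuppressant or antimalarial agents, with no time window. A prohibited oral increase at Day 80 that has resolved by Day 120 is a medication failure yet meets the endpoint. A taper during Days 150–210 breaks the hold rule yet meets it too. The two overlap heavily on oral escalation in Days 120–210 and differ elsewhere.

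*The endpoint reads the same in both arms whatever the drug does.* That assumes treatment cannot change escalation. If fewer patients escalate on active drug, the endpoint can detect it, as the 63% row shows. That is avoided escalation, which may be worth reporting, but it is not reduction.

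It is also fair to say that this is one item in a long secondary list in a proof-of-concept trial sized on SRI-4, and that Section 8.2.4 leaves missing-data and medication-failure handling to the SAP, which was not available for this review. The criterion itself is fixed in the Protocol, however, and an SAP that required a decrease would depart from it.

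**Conclusion.** Wrong as written. The endpoint requires no reduction: a patient with an unchanged dose or on 0 mg throughout is a responder, and this holds on either reading of Section 4.6.1. The endpoint therefore mainly measures absence of CS escalation, largely overlaps the CS part of the medication-failure endpoints, and cannot show steroid sparing.

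The finding that all rule-following paths respond (286 of 286) rests on taking baseline as Day 0 and barring any dose above it after Day 60. The rejection probabilities illustrate assumed rates and are not predictions. The primary analysis is untouched. The correction should be made because the label misdescribes the result that would be reported.

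**What to change.** Preferred: analyse the endpoint in patients taking oral CS at Day 0, and require a dose below the Day 0 dose that is maintained through Day 210. Align the derivation with the tapering windows in Section 4.6.1, so that a taper made in Days 120–150 and then held can count. Requiring the decrease to be present by Day 120 would miss those patients. The size of decrease that qualifies is a clinical choice for the sponsor.

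Alternative: keep the criterion, rename the endpoint as no increase in oral CS above the Day 0 dose, and report change in daily dose alongside.

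Separately, the burst-taper statement and the no-increase statement in Section 4.6.1 should be reconciled. Which should prevail is not a statistical question.

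Cost: wording and derivation only. Concomitant medication is already recorded at every visit, and no dosing rule needs to change for the endpoint fix. The preferred version has a smaller denominator, a lower reported rate and lower power: for an assumed 40% vs 20%, about 50% if half the patients are on CS, rather than 77% with all 132.

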3 STUDY PLAN

3.1 Study Design

This is a Phase 1b/2 combined, randomized, multicenter, double-blind, placebo-controlled trial to study the clinical efficacy, safety, and PK of SC doses of BOS161721 in adult patients with moderately to severely active SLE. After successfully completing a screening phase, eligible patients will be randomized to a specified dose of BOS161721 or placebo. The dosing schedule will be monthly.

The trial will consist of 2 double-blinded portions: MAD Phase 1b and POC Phase 2. Patients may receive a total of 7 SC monthly doses of study drug on Days 0, 30, 60, 90, 120, 150, and 180, followed by safety follow-up visits at Days 210, 240, and 270.

SLE disease activity assessment data will be centrally reviewed by medical monitor and sponsor to ensure the scores are clinically meaningful and compliant with specific definition. The scope of responsibility includes, but is not limited to, review and confirmation of “A” and “B” BILAG system organ disease, confirmation of clinical components of the SLEDAI-2K score at screening and during the study, and cross-validation of the instruments used in this study to assess the disease activity. Further details on the content and methods of data reports by the medical monitor and sponsor will be outlined in the Medical Data Review Plan along with the processes and procedures that will be followed.

